Measures of acute changes in metabolism and energy homeostasis will be performed the morning of the liver biopsy. The primary comparisons will be made using an intention-to-treat analysis of the change in the (a) metabolic and (b) energy homeostatic measures from baseline. (c) compartment volumes by MRI. Secondary outcomes measures will include changes in clinical and histologic features of NAFLD as assessed by liver enzymes and the NAFLD Activity Score (NAS), as determined from standardized histologic scoring of liver biopsies. This study will be conducted in compliance with the protocol, Good Clinical Practice (GCP), and all applicable regulatory requirements.

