## 10. Statistical design and analysis

Coefficients of variance (CV) will be used to evaluate reproducibility of MRS/MRI baseline measures. Intra-class correlations (ICC) will be used to measure absolute test-retest baseline measure reliability for the test-retest subjects. ICCs will be calculated with a model that separates subject, voxel, measurement and error variances using an analysis of variance (ANOVA) method. We will include a number of multi-factorial random effects models (66, 67) which use a restricted maximum likelihood (REML) algorithm to prevent negative variance terms. The ANOVA model for metabolite estimates across all subjects will be  $M_{ijk} = \mu + S_i + V_{ij} + N_k + e_{ijk}$  where  $\mu$  is the average across all voxels,  $S_i$  = subject,  $V_{ij}$  = voxel and  $N_k$  = scan random effects, respectively and  $e_{ijk}$  is residual error. For ICC in individual subjects, we leave out the  $S_i$  term. ICCs for test-retest measures will be based on random-effects analysis of the variance models and will be computed as follows:  $ICC = \sigma^2_B / (\sigma^2_B + \sigma^2_w + \sigma^2_e)$  where  $\sigma^2_B$  is generalized between-subject variance of metabolites,  $\sigma^2_w$  is within-subject variance between scans 1 and 2 and  $\sigma^2_e$  is variance due to random noise (68). CVs for test-retest reproducibility will be calculated using  $CV = \sqrt{\sigma^2_w + \sigma^2_e} / \mu$ . Similarly we will obtain CVs from the first 20 subjects in Aim2 and will compare these to the normal population.

Dynamic changes will be characterized in a more *ad hoc* manner. From the metabolite estimates at time  $t$  ( $M_{ijkt}$ ), the following parameters will be measured for each individual (subscript  $i$ ): baseline ( $B_i$  = mean of  $M_{jkt}$ , where  $t$  = prior to fructose challenge), range of change from baseline ( $D_i = B_i - \min(M_{jkt})$  if any), time to maximal change ( $T_i$  = time to reach  $\min(M_{ijkt})$ ), time to baseline recovery ( $R_i$ , if applicable). A 95% confidence interval of baseline will be used to test if the metabolite level is recovered to the baseline. If it does not reach the baseline, we will estimate the baseline based on the assumption of a linear recovery rate. Since metabolite levels will be measured at discrete time points, spline smoothing will be used to fit the curve. These values will be averaged across the cohort of volunteers and simple measures of variance calculated.

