**10.1 Sample size and Statistical Power Consideration:** Assuming 20% change in hepatic ATP and uric acid (i.e. before~ Normal( $1.2, \sigma^2$ ) and after ~ Normal( $1, \sigma^2$ )), one-side test with alpha = 0.15, the power would be i) if  $\sigma^2 = 1$ , power = 0.523 ii) if  $\sigma^2 = 0.8$ , power = 0.629, iii) if  $\sigma^2 = 0.6$ , power = 0.784, iv) if  $\sigma^2 = 0.5$ , power = 0.875.

**10.2 Analytical and Statistical Approach:** We will test if the acute fructose challenge alters hepatic ATP in healthy volunteers compared to those with NAFLD and whether changes MR parameters and/or energy homeostasis can predict the histologic severity of NAFLD.

**10.3 Management of Missing data:** The occurrence of missing data in this trial is expected to be low. We estimate that careful selection of patients during the screening phase and the consent process should result in no more than 10% missing data from patients who drop out before completing the study.

**10.4 Justification of sample size:** A total of 67 patients will be included to compare the efficacy of acute fructose challenge on the metabolic and energy homeostasis changes in patients with NAFLD.

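### The powers in section 10.1 appear to treat before and after as two independent samples, although the plan analyses each patient's change from baseline; the pairing and the SD/variance label must be corrected together

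*Combined protocol and SAP*

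**What the plan says.** Section 10.1 starts from "Assuming 20% change in hepatic ATP and uric acid" and models it as "before~ Normal( $1.2, \sigma^2$ ) and after ~ Normal( $1, \sigma^2$ )), one-side test with alpha = 0.15". It then lists four cases, beginning with "\sigma^2 = 1$ , power = 0.523"; the other three are 0.8 with power 0.629, 0.6 with 0.784, and 0.5 with 0.875. It states no correlation between the two occasions, no SD of the change, no test and no sample size beside these powers.

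Section 10.3 allows for up to 10% missing data. Section 10.4 says: "A total of 67 patients will be included to compare the efficacy of acute fructose challenge". Sections 3.1, 3.4 and 8.1 give 70 patients with NAFLD.

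Elsewhere the comparison is within patients. Section 3.1 says: "The primary comparisons will be made using an intention-to-treat analysis of the change in the (a) metabolic and (b) energy homeostatic measures from baseline". Sections 5 and 9.4 take MR data and blood before fructose, and again over or at the end of the following hour, in the same subject. For the dynamic MR response, section 10 says that "the following parameters will be measured for each individual", and one of these is the drop from that individual's own baseline to the lowest later value.

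**The concern.** Two measurements on one person in one session are normally correlated, and the variance of their difference depends on that correlation. A calculation with two separate normal distributions and no correlation omits that term. If the printed powers come from an independent-samples formula, they describe a design with different people before and after, which is not this trial.

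The four powers are the only quantitative support for the sample size. If they belong to another test, the reader cannot tell what power the planned within-patient comparison has, or judge the lenient one-sided error rate of 0.15 against it.

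**Working it through.** **Inputs.** Difference 1.2 − 1.0 = 0.2, one-sided alpha 0.15 and listed values v = 1, 0.8, 0.6, 0.5 (section 10.1); 67 patients (10.4); 10% missing (10.3). Evaluable patients: 67 × 0.9 = 60.3, taken as 60. The documents give no correlation ρ, so 0.2, 0.5 and 0.8 are assumed as a range.

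**Step 1: reproduce the printed powers.** For two independent samples of n each, power comes from the noncentral t with df = 2n − 2 and noncentrality 0.2 / (s√(2/n)). With n = 60 and s = 1 this is 0.2 / 0.1826 = 1.095, on 118 df.

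| Calculation | case i | ii | iii | iv |
|---|---|---|---|---|
| Printed in 10.1 | 0.523 | 0.629 | 0.784 | 0.875 |
| 60 v 60, v used as SD | 0.5225 | 0.6292 | 0.7838 | 0.8748 |
| 60 v 60, v used as variance (s = √v) | 0.523 | 0.574 | 0.646 | 0.695 |

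The first reconstruction matches all four figures. Samples of 59, 61, 67 or 70 per occasion do not. With the values used as variances, no common n from 5 to 199 fits.

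**Step 2: rival reconstructions.** A paired t-test on 60 patients with ρ = 0 gives 0.5215/0.6280/0.7826/0.8738. That is close, and it also gives pairing no credit. A paired t-test on 30 patients with ρ = 0.505 gives 0.5216/0.6281/0.7827/0.8739, within about 0.001 of print, but it needs 30 patients where section 10.4 has 67.

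**Step 3: power for the plan's own comparison.** For a paired t-test, SD of change = s√(2(1 − ρ)), noncentrality = 0.2√n / SD of change, df = n − 1. With n = 60, s = 1 and ρ = 0.5, the SD of change is 1 and the noncentrality is 0.2 × 7.746 = 1.549, on 59 df; power is 0.693. At one-sided alpha 0.15:

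| Listed values taken as | ρ | case i | ii | iii | iv |
|---|---|---|---|---|---|
| SDs | 0.2 | 0.572 | 0.687 | 0.840 | 0.920 |
| SDs | 0.5 | 0.693 | 0.814 | 0.937 | 0.980 |
| SDs | 0.8 | 0.920 | 0.978 | 0.999 | 1.000 |
| Variances | 0.2 | 0.572 | 0.628 | 0.705 | 0.754 |
| Variances | 0.5 | 0.693 | 0.754 | 0.830 | 0.874 |
| Variances | 0.8 | 0.920 | 0.954 | 0.983 | 0.992 |

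On the SD reading every entry exceeds print. On the variance reading at ρ = 0.2, case ii equals print to within 0.001, while cases iii and iv fall short by 0.784 − 0.705 = 0.079 and 0.875 − 0.754 = 0.121. At ρ = 0.5, case iv is level with print (0.874 against 0.875).

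**Step 4: stricter alpha.** Paired, n = 60, ρ = 0.5, listed values as SDs: one-sided 0.05 gives 0.455/0.606/0.818/0.922; one-sided 0.025 gives 0.331/0.478/0.719/0.862.

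**Step 5: which change to test.** Section 10's drop is baseline minus the minimum of a series. The minimum of several noisy readings lies below their mean even when nothing has changed. In simulations with no effect (assumed: 3 baseline readings, 5 or 10 later readings, ρ 0.5 or 0.8, 60 patients), a one-sample t-test of this drop at one-sided 0.05 rejected in 100% of runs. The SD formula in step 3 does not apply to it either.

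**The case against.** The strongest reply is that section 10.1 names neither test nor n, so the independent-samples reading is a reconstruction. The paired test on 30 patients fits nearly as well, 30 is the size of the healthy cohort, and the text just before 10.1 ends with averages over the volunteers. This stands as a reason to say that the plan appears to ignore pairing. It does not rescue the figures: 60 v 60 fits slightly better, follows from 67 less 10%, and uses sigma as 10.1 defines it, for the before and after values. A calculation on 30 patients would not describe the 67 either.

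Three stronger readings are tempting, and the documents do not support them.

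- A reader might infer that ignoring pairing makes the printed powers too low. That holds if the listed values are SDs; on the plan's own notation they are variances, and then some printed powers are too high.
- A reader might infer that 0.15 was chosen because power looked poor, and that pairing allows 0.05 or 0.025. The plan gives no reason for 0.15, and section 3.5 calls the study exploratory. Step 4 shows that at ρ = 0.5 power is below 80% in two of four cases at 0.05 and in three of four at 0.025.
- A reader might infer that the analysis itself will have the wrong error rate. An independent-samples test on paired data would have an actual error rate of about 0.12, 0.07 or 0.01 at ρ 0.2, 0.5 or 0.8 against a nominal 0.15. No section plans that test, and sections 3.1 and 10 work with change from baseline.

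It can also be said that section 10.2 compares healthy volunteers with NAFLD, which a before-after table does not size. That is correct, and the restated section should say so.

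**Conclusion.** The point holds as a fault in the power statement, not in the planned analysis. The four powers in 10.1 are very probably those of a two-sample t-test on 60 v 60 with the listed values as SDs, whereas the plan compares each patient with his or her own baseline. They therefore do not describe the plan's comparison.

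The size depends on two things that the documents leave open: ρ, and whether the listed values are SDs or variances. At n = 60 and alpha 0.15, with ρ from 0.2 to 0.8, case i runs from 0.572 to 0.920 against 0.523 printed. Case iv runs from 0.920 to 1.000 (SDs) or from 0.754 to 0.992 (variances) against 0.875 printed. No overall direction can be claimed. The conclusion assumes 60 evaluable patients, a common SD on both occasions and a change measured at a fixed time.

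**What to change.** - In 10.1, replace the four powers with those of a paired t-test on each patient's change between baseline and a prespecified post-fructose time, for example the 1-hour uric acid sample. Do not use the baseline-minus-minimum drop of section 10 for this test.
- State n = 60 evaluable of 67, and whether the listed values are SDs or variances.
- Show the SD of change as SD × √(2(1 − ρ)) for ρ 0.2, 0.5 and 0.8, and update it from the Aim 1 volunteers, who receive the same challenge.
- Name the paired test in 10.2 for the within-patient change.
- Show power at one-sided 0.05 and 0.025 beside 0.15, and choose or justify alpha once the SD of change is known.
- State that this table does not power the comparison of healthy volunteers with NAFLD in 10.2.

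The cost is a recalculated table and rewording of 10.1 and 10.2, with no added patients or procedures. The drawback is that power becomes a range, and some figures may be lower than those now printed.

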## 3. Study design

### 3.1 Design overview

The proposed open label study is single-center randomized, phase II clinical trial designed to address the following specific aims:

- a) **To optimize an MR protocol to characterize the range and rates of *baseline and dynamic* measures of metabolism and energy homeostasis following an acute IV fructose challenge.** Volumetric and quantitative measures of hepatic lipid deposition, energy levels, and water homeostasis will be characterized in normal volunteers to determine typical ranges and coefficients of variation for each technique.
- b) **To differentiate the baseline and dynamic changes of metabolic and energy homeostasis following an acute IV fructose challenge in patients with biopsy-proven NAFLD.** MR-based measurements from the Aim 1 protocol will be correlated to clinical measures of metabolism, energy homeostasis and histologic disease activity before, during and at 4 and 24 hours following IV fructose challenge in regions co-localized and distant from biopsy.

A cohort study of healthy volunteers (n=30) and patients with NAFLD (n=70) will be enrolled. Healthy volunteers will have no evidence of chronic liver disease (normal liver enzymes and normal liver imaging and/or a liver biopsy performed for clinical evaluation of liver disease but whose pathology results note no pathologic abnormalities). Patients with suspected NAFLD who will undergo a standard-of-care liver biopsy, or who have had a historical biopsy within 6

months of the Screening visit, will have both acute intravenous fructose challenge for assessing baseline and post-dietary intervention *static and dynamic* measures of metabolism and energy homeostasis. Co-localization of liver biopsy with MRI to optimize / assess MRI measures of the histologic features of NAFLD will be performed to develop MRI as a surrogate “biomarker” for liver biopsy. With the exception of the liver biopsy, no accurate non-invasive biomarker for disease activity currently exists.

Screening for eligibility and collection of baseline data will span up to 8 weeks. Patients who have had a liver biopsy showing NAFLD within 6 months of the Screening visit or patients who will be undergoing a standard of care percutaneous liver biopsy for NAFLD will be consented.

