### 3.2 Population

Participants at least 18 years of age, both healthy controls and those with suspected NAFLD.

**3.4 Sample size:** 30 healthy controls and 70 subjects with biopsy-proven NAFLD

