## 8. Patient Selection

**8.1 Recruitment:** Thirty healthy controls and 70 patients with NAFLD will be recruited from the Duke Liver Clinics. Eligible patients will be identified and recruited by the principle investigator and/or sub-investigator. Recruitment into the study will be performed without regard to gender or ethnicity as any patient with suspected NAFLD will be considered eligible if all inclusion and no exclusion criteria are met.

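### Section 10.1 appears to label standard deviations as variances, so its four powers do not follow from the stated inputs; its n and test are not stated, and 67 patients is not reconciled with 70

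*Combined protocol and SAP*

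**What the plan says.** Section 10.1 opens with "Assuming 20% change in hepatic ATP and uric acid (i.e. before~ Normal" and models the values as normal with mean 1.2 before and 1 after, with a common variance. It continues "one-side test with alpha = 0.15, the power would be i) if" and gives four cases, each labelled as a value of sigma squared: 1 (power 0.523), 0.8 (0.629), 0.6 (0.784) and 0.5 (0.875). It states no sample size, does not say whether the test is paired or independent, and gives no before/after correlation.

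The nearby sections bear on the missing n:

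- Section 10.3 expects that recruitment and consent procedures "should result in no more than 10% missing data from patients who drop out before completing the study".
- Section 10.4 says "A total of 67 patients will be included to compare the efficacy of acute fructose challenge".
- Section 3.1 says "A cohort study of healthy volunteers (n=30) and patients with NAFLD (n=70) will be enrolled", section 3.4 gives "30 healthy controls and 70 subjects with biopsy-proven NAFLD", and section 8.1 says "Thirty healthy controls and 70 patients with NAFLD will be recruited".

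Section 10.2 states the planned comparison: "We will test if the acute fructose challenge alters hepatic ATP in healthy volunteers compared to those with NAFLD".

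**The concern.** With means, alpha and sample size fixed, power depends on the spread only through the standard deviation. Going from a variance of 1 to a variance of 0.5 raises the standardised effect by a factor of 1.41. The printed powers rise much faster than that. They behave as if the standard deviation itself had been halved.

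No other power figures are given in the plan. A reader who takes the labels literally uses the wrong spread in three of the four cases; the first case cannot reveal the problem, because a variance of 1 is also a standard deviation of 1. Nor can the figures be checked directly, because section 10.1 gives no n and no test, and the patient numbers elsewhere (67 and 70) disagree. Before and after values come from the same patients, so the power of the real comparison also depends on a correlation that the plan does not state.

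**Working it through.** **Inputs (section 10.1).** Difference 1.2 − 1 = 0.2; one-sided alpha 0.15, so z(0.85) = 1.036; labelled values 1, 0.8, 0.6, 0.5; powers 0.523, 0.629, 0.784, 0.875.

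**Step 1: a check that needs no n.** Under the normal approximation each power fixes a standardised effect, z(0.85) + z(power):

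- 1.036 + 0.058 = 1.094
- 1.036 + 0.329 = 1.366
- 1.036 + 0.786 = 1.822
- 1.036 + 1.150 = 2.187

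The effect is proportional to 1/SD. Any sample size or correlation common to the four cases cancels when each effect is divided by the first.

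| Case | Ratio implied by printed powers (limits from rounding) | If values are SDs | If values are variances |
|---|---|---|---|
| ii | 1.248 (1.246–1.251) | 1/0.8 = 1.250 | 1/√0.8 = 1.118 |
| iii | 1.665 (1.662–1.669) | 1/0.6 = 1.667 | 1/√0.6 = 1.291 |
| iv | 1.999 (1.994–2.003) | 1/0.5 = 2.000 | 1/√0.5 = 1.414 |

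The SD reading lies inside all three intervals and the variance reading outside all three.

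**Step 2: the n implied by each power.** For two independent samples, n per sample = 2 × (effect × SD / 0.2)². Case iv as an SD gives 2 × (2.187 × 0.5 / 0.2)² = 59.8. Case iv as a variance gives 2 × 2.187² × 0.5 / 0.04 = 119.6.

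- Read as SDs: 59.9, 59.7, 59.8, 59.8.
- Read as variances: 59.9, 74.6, 99.6, 119.6.

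**Step 3: reproducing the printed figures.** Two-sample t-test, noncentral t, one-sided alpha 0.15:

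| Reading | n per sample | i | ii | iii | iv | Largest miss |
|---|---|---|---|---|---|---|
| Printed | not stated | 0.523 | 0.629 | 0.784 | 0.875 | |
| SD | 59 | 0.519 | 0.625 | 0.779 | 0.871 | 0.005 |
| SD | 60 | 0.5225 | 0.6292 | 0.7838 | 0.8748 | 0.0005 |
| SD | 61 | 0.526 | 0.634 | 0.788 | 0.879 | 0.005 |
| SD | 67 | 0.547 | 0.658 | 0.813 | 0.899 | 0.029 |
| SD | 70 | 0.557 | 0.670 | 0.824 | 0.907 | 0.041 |
| Variance | 60 | 0.523 | 0.574 | 0.646 | 0.695 | 0.180 |
| Variance | 86 (best) | 0.608 | 0.666 | 0.743 | 0.793 | 0.085 |

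Under the variance reading, letting n and correlation vary together in a paired test still leaves a miss of about 8.4 points.

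**Step 4: where 60 may come from.** 60 / 0.9 = 66.7, rounded up to 67; equally 67 × 0.9 = 60.3. So 60 is probably the 67 of section 10.4 less the 10% of section 10.3. The plan does not say so. The same step from 70 gives 70 × 0.9 = 63, for which the SD reading gives 0.533, 0.642, 0.797 and 0.886, not the printed figures.

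**Step 5: allowing for pairing.** The SD of a within-person difference is SD × √(2(1 − correlation)). Paired t-test, 67 patients:

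| Reading | Correlation | i | ii | iii | iv |
|---|---|---|---|---|---|
| SD | 0 | 0.546 | 0.657 | 0.812 | 0.898 |
| Variance | 0 | 0.546 | 0.600 | 0.674 | 0.724 |
| Variance | 0.5 | 0.724 | 0.784 | 0.857 | 0.898 |

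Under the variance reading, all four printed powers are reached only at a correlation of about 0.44 or more with 67 patients, or about 0.50 with 60.

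**The case against.** The strongest reply is that this is a notation slip with no consequence. If SDs were meant, the powers are right, and a paired test in 67 patients exceeds every printed value even at zero correlation. The study is described in section 3.5 as exploratory, and section 10.1 offers a range of scenarios rather than one power target. This largely stands as to consequence: the shortfalls of 5.5 to 18.0 points apply only if variances were meant, which is the less likely reading. It does not make the text correct. The figures still cannot be obtained from the inputs as labelled, and only the sponsor can confirm which reading was intended.

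A second reply is that 60 per sample is an inference. That is so. A paired test in 30 patients, with the four values as SDs of the difference, gives 0.519, 0.626, 0.780 and 0.872, within 0.4 points of print. Two samples of 60 fit better, to three decimals, but the near-tie is a reason to state the test. Both fits need the SD reading.

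A third reply is that recruiting 70 comfortably covers an analysis of 67. It may, and no shortfall follows. But no section links the two numbers.

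Finally, sections 10.1 and 10.4 already point to before/after change in patients with NAFLD, so a sentence on the healthy versus NAFLD comparison is a clarification. That is fair. It is still useful, because section 10.2 names that comparison and the plan gives no power for it.

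**Conclusion.** The concern holds. The four powers in section 10.1 are inconsistent with their labels as variances, whatever common sample size or correlation is assumed, and they agree with the same numbers read as standard deviations. That conclusion rests only on the stated means and the one-sided alpha of 0.15. That the calculation used two independent samples of 60, and that 60 came from 67 less 10%, is likely but inferred.

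If SDs were meant, the powers stand under that model and only the label is wrong. If variances were meant, power at 60 independent per sample falls to 0.574, 0.646 and 0.695 in the last three cases. A paired analysis of 67 would then give 0.55 to 0.72 at zero correlation and 0.72 to 0.90 at 0.5. The difference between 67 and 70 remains unexplained in the current text. This should be fixed, but it is not a reason to enlarge the study on the likely reading.

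**What to change.** - In section 10.1, relabel the four values as standard deviations. If variances were meant, recompute the four powers instead.
- In the same place, state the n behind the powers, whether the test is paired or independent, and the assumed within-person correlation. If n is 67 less 10%, say so.
- Reconcile the 67 in section 10.4 with the 70 in sections 3.1, 3.4 and 8.1, for example by stating which is the recruitment target and which the number assumed for the calculation.
- Add one sentence that these powers concern a before/after change and do not cover the healthy versus NAFLD comparison in section 10.2.

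The cost is one symbol and two or three sentences. Relabelling implies no extra patients. If variances were meant, four powers must be recalculated, and they may look less favourable depending on the correlation assumed.

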### 1.2 Principal objectives:

- To define whether baseline and dynamic changes in hepatic ATP during a fructose challenge are associated with NAFLD and/or liver disease severity in patients with NAFLD.
- To assess whether such factors can be measured using magnetic resonance (MR) biomarkers

We will measure *baseline and dynamic* changes in metabolism, energy homeostasis and MR biomarkers in healthy volunteers and patients with biopsy-proven NAFLD. The effect of acute fructose challenges on changes in metabolism and energy homeostasis will be assessed in a cohort of patients with NAFLD.

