### 2.3 Fructose Alters Energy Homoeostasis and Causes Hyperuricemia

[figure not shown]
In support of our hypothesis that ATP depletion underlies liver injury in patients with NAFLD, our group has demonstrated that patients with biopsy-proven NAFLD have increased hepatic mRNA expression of KHK compared to matched controls (17). Indeed, in human pilot studies, intravenous (IV) fructose administration is associated with hepatic ATP depletion (20, 21) which can be assessed by  $^{31}\text{P}$  magnetic resonance spectroscopy (MRS) (22). Reduced hepatic ATP stores are more prevalent in overweight and obese subjects than in lean subjects (23). Furthermore, recovery from fructose-induced ATP depletion was found to be delayed in patients with NAFLD ( $n=8$ ) (24). However, a limitation to this existing work is the small sample size and the inability to assess a cause-effect relationship(s) between BMI, NAFLD, energy homeostasis, and histologic features of liver injury. In liver cells, ATP depletion could perpetuate chronic liver injury by making fatty hepatocytes less proliferative. Hepatic ATP depletion also encourages the expansion of liver progenitor populations (25), causes arrest in protein synthesis, induces inflammatory and prooxidative changes (26, 27), increases endoplasmic reticulum stress, promotes activation of stress-related kinases, induces mitochondrial dysfunction, and increases

apoptotic activity (28-30). This supporting data suggests that fructose may be associated with NAFLD, NASH, and progressive fibrosis. Further, a study by Loguercio *et al.* demonstrated that increased uric acid levels above the basal level after IV fructose infusion was significantly higher ( $p < 0.01$ ) in patients with cirrhosis (3 mg/dl) and NASH (1.9 mg/dl) than in healthy controls (1.2 mg/dl) (31). This effect was completely reversed by fructose 1,6-diphosphate which could replenish the ability to resynthesize ATP from ADP. Therefore, an IV fructose challenge could effectively differentiate healthy subjects, from chronic hepatitis, from cirrhosis (31).

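### The powers in 10.1 are for a before-after shift and do not apply to the healthy v NAFLD test in 10.2, for which no power is stated

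*Combined protocol and SAP*

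**What the plan says.** Section 10.1 gives the power statement: "Assuming 20% change in hepatic ATP and uric acid", with a mean of 1.2 before "and after ~ Normal" with mean 1, and a "one-side test with alpha = 0.15". For variances printed as 1, 0.8, 0.6 and 0.5 it reports powers of 0.523, 0.629, 0.784 and 0.875. It gives no sample size, names no group and does not say whether the test is paired.

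Section 10.2 then states the test: "We will test if the acute fructose challenge alters hepatic ATP in healthy volunteers compared to those with NAFLD". It adds prediction of histologic severity from MR and energy measures. Objective 1.2 has the same two parts: "To define whether baseline and dynamic changes in hepatic ATP during a fructose challenge are associated with NAFLD and/or liver disease severity".

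Section 3.4 sets the groups at "30 healthy controls and 70 subjects with biopsy-proven NAFLD". Section 10.4 says "A total of 67 patients will be included to compare the efficacy of acute fructose challenge" and ties that number to changes in patients with NAFLD. Section 10.3 expects at most 10% missing data. No section gives a between-group difference in change, an SD of change, a before-after correlation, or a power for healthy v NAFLD.

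**The concern.** The plan powers one contrast and describes a test of another. A before-after shift asks whether fructose changes ATP. Section 10.2 asks whether that change differs between healthy people and patients. The second question has a different standard error, because the groups are 30 and 70 and the outcome is a change. It usually also has a smaller effect, because any response in controls is subtracted. Section 2.3 reports that controls do respond, at least in uric acid: the rise was higher "in patients with cirrhosis (3 mg/dl) and NASH (1.9 mg/dl) than in healthy controls (1.2 mg/dl").

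A reader who meets 0.52 to 0.88 directly above the only group comparison in section 10 could attach those figures to it. If the true power is lower, a null comparison could be over-read as evidence that NAFLD does not alter the ATP response.

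**Working it through.** **Inputs from the documents.** Difference 0.2 (1.2 less 1.0); one-sided alpha 0.15; spread values 1, 0.8, 0.6, 0.5 (10.1). Groups 30 and 70 (3.4). Loss up to 10% (10.3), giving 27 v 63. **Assumed:** the before-after correlation ρ and the response in controls.

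**Step 1: reproduce the printed powers.** Power is taken from the noncentral t distribution, approximately Φ(δ/SE − 1.036). For two unpaired sets of n, SE = SD × √(2/n). With n = 60 and SD 1, SE = √(2/60) = 0.1826 and 0.2/0.1826 = 1.095, so power is about Φ(0.059) = 0.52.

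| 60 v 60, unpaired | 1 | 0.8 | 0.6 | 0.5 |
|---|---|---|---|---|
| Printed | 0.523 | 0.629 | 0.784 | 0.875 |
| Values used as SDs | 0.523 | 0.629 | 0.784 | 0.875 |
| Values used as variances, as labelled | 0.523 | 0.574 | 0.646 | 0.695 |

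With the values as SDs all four match to three decimals, and n = 60 agrees with 10.4 less 10% (67 × 0.9 = 60.3). A one-sample test on 30 pairs, with the values as the SD of the change, comes close but does not match (0.519, 0.626, 0.780, 0.872). With the values as variances, no single n gives the four powers. None of these is a 30 v 70 comparison.

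**Step 2: the 10.2 contrast.** This is a difference in mean change between groups:

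SE = SD × √(2(1−ρ)) × √(1/30 + 1/70), where √(1/30 + 1/70) = 0.2182.

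The equivalent equal group size is 2/(1/30 + 1/70) = 42, against 60 in Step 1. At ρ = 0.5 the SD of change equals the SD. For SD 1, 0.2/0.2182 = 0.917 and power is about Φ(−0.120) = 0.45.

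| Healthy v NAFLD, one-sided 0.15 | 1 | 0.8 | 0.6 | 0.5 |
|---|---|---|---|---|
| 30 v 70, difference 0.2 (controls do not respond), ρ 0.5 | 0.451 | 0.542 | 0.687 | 0.786 |
| 27 v 63, difference 0.2, ρ 0.5 | 0.433 | 0.519 | 0.658 | 0.757 |
| 30 v 70, difference 0.1 (controls respond half as much), ρ 0.5 | 0.281 | 0.321 | 0.392 | 0.451 |
| 30 v 70, difference 0.2, ρ 0.5, values as variances | 0.451 | 0.494 | 0.557 | 0.601 |
| 30 v 70, difference 0.2, ρ 0 | 0.348 | 0.410 | 0.516 | 0.601 |
| 30 v 70, difference 0.2, ρ 0.8 | 0.659 | 0.779 | 0.915 | 0.968 |

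**Step 3: where the shortfall ends.** Setting the Step 2 ratio δ/SE equal to that of Step 1 gives 1 − ρ = [(2/60) / (2 × (1/30 + 1/70))] × (δ/0.2)² = 0.35 × (δ/0.2)².

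- δ = 0.2: ρ = 0.65. At 27 v 63 it is 0.685.
- δ = 0.1: ρ = 1 − 0.35 × 0.25 = 0.91.

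**Step 4: are the printed powers right for change within NAFLD?** Before and after values in the same patients are paired, so SE = SD × √(2(1−ρ)) / √60. With the values as SDs:

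- ρ = 0: 0.522, 0.628, 0.783, 0.874.
- ρ = 0.5: 0.693, 0.814, 0.937, 0.980.

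The printed figures therefore describe the within-NAFLD test only if the correlation is about zero.

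**The case against.** The strongest reply is that 10.1 says before and after openly, and that the plan's emphasis lies within NAFLD. Section 3.1 makes the primary comparisons changes from baseline. Section 3.6 places the primary outcome in patients with biopsy-proven NAFLD, with histology as the primary predictor. Section 9.1 gives controls the role of reference and optimization values, and 3.5 calls the study exploratory. This stands to the extent that a reader should not infer that healthy v NAFLD is the contrast on which the trial will conclude; the documents do not rank the contrasts. It does not remove the gap, because 10.2 commits to the group test and objective 1.2 asks for it.

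A second reply is that the correlation may be high. Baseline is a mean of several acquisitions (section 10), and Appendix A says the patient is not repositioned between acquisitions for different nuclei. This also stands. A reader might infer that 30 v 70 must fall short of the printed powers, but above a correlation of about 0.65, with the full 0.2 difference, it exceeds them.

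A third concerns the uric acid figures in section 2.3. Scaling 0.2 by them gives 0.2 × (1 − 1.2/1.9) = 0.074 and power of 0.24 to 0.36 at ρ = 0.5. It is tempting to treat this as the real power. The documents do not support that: the ratio is for uric acid rather than ATP, comes without an SD, and uses NASH only. The cirrhosis figure in the same sentence gives 0.2 × (1 − 1.2/3) = 0.12, and section 8.2 lets NASH-related cirrhosis enrol. The 0.074 case is illustrative only.

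**Conclusion.** The concern holds in a limited form. It is certain from the text that the only stated powers are for a before-after shift, that n, group and test are not given, and that the healthy v NAFLD test has no stated power. It is also certain that the printed values match 60 v 60 only when the quantities labelled as variances are used as SDs.

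The size of the shortfall is conditional. With the values as SDs, ρ = 0.5 and no response in controls, power is 7 to 10 percentage points below the printed figures (0.523 − 0.451 = 0.072; 0.784 − 0.687 = 0.097). If controls respond half as much, it is 0.281 to 0.451. Both the correlation and the control response are assumptions. This should be fixed, but it does not show that the enrolment is wrong or that the trial cannot meet its objective.

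**What to change.** In 10.1:

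- State n, the group, the test, and whether 1, 0.8, 0.6 and 0.5 are SDs or variances. Reconcile the 67 in 10.4 with the 70 in 3.4.
- Do not simply relabel the printed powers as within-NAFLD. Recompute that figure as a paired test with a stated correlation.
- Add the power, or the detectable difference, for the 10.2 contrast: difference in mean change, 30 v 70 and 27 v 63, over a stated range of control response and correlation.
- Say which contrast is primary: change within NAFLD, healthy v NAFLD, or association with histologic severity.

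The cost is wording and one short recalculation, with no change in enrolment. The downside is that the stated power for the group comparison becomes less favourable under most of the inputs tried here.
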